**LIST OF ABBREVIATIONS AND DEFINITION OF TERMS**

Abbreviation	Definition
AE	Adverse Event
$\lambda_z$	First-order terminal elimination rate constant
%CV	Percent coefficient of variation
Ae	Cumulative amount of unchanged study drug excreted into the urine
Ae 0-48	Cumulative amount of unchanged study drug excreted into the urine from time 0 to 48 hours postdose
AUC	Area under the concentration-time curve
AUC 0-48	Area under the concentration-time curve from time 0 to 48 hours postdose
AUC 0-inf	Area under the concentration-time curve from time 0 extrapolated to infinity time
AUC 0-last	Area under the concentration-time curve from time 0 to the last quantifiable concentration
BMI	Body mass index
BP	Blood pressure
CL/F	Apparent total body clearance after SC administration
CL r	Renal clearance
C max	Maximum observed concentration directly from data
CNS	Central nervous system
CRO	Contract research organization
ECG	Electrocardiogram
eCRF	Electronic case report form
EDC	Electronic data capture
eGFR	Estimated glomerular filtration rate
Fe 0-48	Fraction of the study drug excreted into the urine from time 0 to 48 hours
FIH	First-in-human
GI	Gastrointestinal
GLP	Good Laboratory Practice
GM	Geometric mean
ICF	Informed consent form
IL	Interleukin
IRB	Institutional Review Board
SC	Subcutaneous
KIM-1	Kidney injury molecule-1
LLOQ	Lower limit of quantification
MedDRA	Medical Dictionary for Regulatory Activities

Abbreviation	Definition
NAC	N-acetyl-cysteine
NGAL	Neutrophil gelatinase-associated lipocalin
NOAEL	No observed adverse effect level
PAMAM	Polyamidoamine
PK	Pharmacokinetic
SAE	Serious adverse event
SAP	Statistical Analysis Plan
SD	Standard deviation
SOC	System organ class
SRC	Safety review committee
$t_{1/2}$	Terminal elimination half-life
TEAE	Treatment-emergent adverse event
$t_{max}$	Time to reach maximum observed concentration directly from data
$V_z$	Volume of distribution after IV administration
WHO	World Health Organization

## 1. INTRODUCTION

This statistical analysis plan (SAP) provides a detailed, technical elaboration of the statistical analysis of safety, pharmacokinetic (PK) and pharmacodynamic (PD) data as described in the study protocol OP-101-003 Version 2.0 dated 17 March 2020. Specifications for tables, listings, and figures are contained in a separate document. Any deviation from this analysis plan will be substantiated by sound statistical/PK rationale and will be documented in the final clinical study report.

## 2. STUDY OBJECTIVES

### 2.1 Primary Objective

The primary objective is to evaluate the safety and tolerability of OP-101 after single subcutaneous doses in healthy subjects.

### 2.2 Secondary Objectives

The secondary objective is to determine the pharmacokinetic (PK) profile of OP-101 after single SC doses in healthy subjects.

## 3. STUDY PLAN OVERVIEW

[figure not shown]
### 3.1 Study Design

This is a Phase 1, open-label, single-ascending dose study to evaluate the safety, tolerability, and PK of OP-101 after subcutaneous administration in up to 8 healthy subjects at 1 site in Australia. This study will consist of a 21-day Screening Period, a 2-day Treatment Period, and Follow-up Visits on Days 8 and 15. Subjects will sign an informed consent form (ICF) before any study procedures are performed and must meet all of the inclusion and none of the exclusion criteria to participate in the study. Eligible subjects will be admitted to the investigational site on Day -1, dosed on Day 1, and discharged on Day 3

[Figure 1](#) presents the cohort dosing schematic. There will be up to 2 separate and sequential **subcutaneous Dose** cohorts (4 mg/kg, and 8 mg/kg) with at least 4 subjects in each cohort who complete Day 15.

**Figure 1. OP-101 Single-Ascending subcutaneous Dose Schedule – Day 1**

1. Cohort enrollment will be separate and sequential with 4 subjects in each cohort who complete Day 15.
  2. Cohort 1 will enroll 4 subjects administered a single SC dose of 4 mg/kg OP-101. Dose escalation to Cohort 2 (8 mg/kg) will be determined by the SRC after review of safety, tolerability and any available PK data through Day 8 of Cohort 1. Cohort 2 will enroll 4 subjects administered a single SC dose of 8 mg/kg.
- PK = pharmacokinetic(s); SRC = safety review committee.

### 3.2 Sample Collection for Pharmacokinetic Analysis

Plasma PK samples will be collected predose, at 30 and at 1, 2, 2.5, 3, 4, 6, 8, 10, 12, 16, 24 and 30-36 hours after dosing, as well as on Day 3 (~48 hr). Blood samples for PK analysis will be obtained within  $\pm 5$  minutes of the scheduled sampling time for sample times  $\leq 1$  hour, within  $\pm 10$  minutes of the scheduled sampling time for sample times  $\leq 12$  hours, and within  $\pm 2$  hours of the scheduled sampling times for sample times  $> 12$  hours.

Urine PK samples will be collected within 60 to 30 minutes prior to dosing (spot sample) and between 0 to 4, 4 to 8, 8 to 12, 12 to 18, 18 to 24, and 24 to 48 hours.

### 3.3 Assessments of Safety

Safety will include adverse event monitoring, clinical laboratory tests (hematology, chemistry, and urinalysis), physical examinations, vital signs (pulse rate, blood pressure [BP], respiration rate, and temperature). Coagulation testing will be performed at screening. Pregnancy testing will be performed at screening and Day -1.

### 3.4 Treatment Groups

There will be 2 separate and sequential SC cohorts with 4 subjects in each cohort. The population will include healthy men and women aged 18 to 65 years, inclusive.

Dose escalation from Cohort 1 to Cohort 2 will be determined by the SRC, consisting of Medical Monitor, the Principal Investigator (or delegate), and Sponsor representative after review of safety, tolerability, and any available PK data through Day 8 of Cohort 1.

Dosing with OP-101 is planned for the cohorts as follows:

- Cohort 1: Single SC dose of 4 mg/kg, and
- Cohort 2: Single SC dose of 8 mg/kg.

### 3.5 Rationale for Dosing

The safety of OP-101 is supported by the completed Phase 1 IV dosing study in healthy volunteers at 20 and 40 mg/kg (3-5 fold higher than the planned SC doses in this study). In

addition, a series of nonclinical studies previously conducted with the active agent in OP-101, NAC, and numerous clinical studies that have been performed with NAC provide further support for the proposed dosing. The overall toxicological profile of OP-101 is expected to be comparable to NAC, which has been evaluated in nonclinical toxicity studies in support of the approval of Acetadote.

Good Laboratory Practice toxicology studies conducted with OP-101 in juvenile and adult rats, incorporating repeat IV doses up to 2000 mg/kg or single IV doses up to 1000mg/kg, have shown no adverse clinical signs or mortality. While a defined NOAEL was not identified in the repeat-dose studies, the single-dose study in adult male rats, demonstrated a NOAEL of 200 mg/kg based upon the absence of single cell necrosis by 2 weeks after dosing and minimal-to-mild severity of this finding noted at earlier time points. Of note, no effects were observed for urinalysis or urine chemistry parameters, and no changes in other urinary biomarkers (kidney injury molecule-1, neutrophil gelatinase-associated lipocalin, albumin, cystatin C, and  $\beta$ -microglobulin) were detected.

From the completed IV dosing study in healthy volunteers it was determined that the clearance of OP-101 was rapid with no detectable drug in the plasma after 24 hours. There were also no clinical adverse events in subjects administered IV doses of 20 or 40 mg/kg OP-101. To enable chronic dosing, SC dosing is being evaluated in this study. The SC dosage formulation has been optimized to enable a single SC dose of 400-500 mg. Higher doses may require two SC injections to achieve the desired dose if necessary. The selection of 4 and 8 mg/kg SC doses enable the majority of the subjects to receive only one injection and is 3-5 fold lower dose than the previous IV study in healthy volunteers. Exposure to NAC at the proposed starting dose and subsequent dose cohorts in this study is orders of magnitude less than that demonstrated to be safe in humans following oral or IV administration.

### **3.6 Dosage Form and Route of Administration**

OP-101 study drug is provided as lyophilized powder in Schott Glass, 5 cc/13 mm Type 1 clear glass vials with West, 13 mm, single vent lyophilizer grey butyl chloride stoppers, and West 13 mm flip-top matte white caps. Each vial is filled to deliver  $500 \pm 50$  mg OP-101. Each vial is reconstituted 0.7 mL sterile water for injection to yield 400 mg/mL OP-101 in 20 mM histidine, pH 5.5 and 80 mg/mL trehalose. Vials of study drug will be supplied in boxes labeled for this study.

Study drug will be administered on Day 1 as a SC injection under the supervision of the site personnel.

Subjects in Cohort 1 will be administered 4 mg/kg OP-101 as a SC injection.

Subjects in Cohort 2 will be administered 8 mg/kg OP-101 as a SC injection.

### 3.7 Randomization and Blinding

This open-label study consists of 2 separate and sequential SC cohorts. Randomization and blinding methods will not be used in this study.

Cohort 1 will enroll 4 subjects administered a single SC dose of 4 mg/kg. Dose escalation from Cohort 1 (4 mg/kg) to Cohort 2 (8 mg/kg) will be determined by the safety review committee (SRC), consisting of the Medical Monitor, the Principal Investigator (or delegate), and Sponsor representative after review of safety, tolerability, and any available PK data through Day 8 of Cohort 1. Cohort 2 will enroll 4 subjects administered a single SC dose of 8 mg/kg.

If an eligible subject is not used in the first cohort and is outside the screening window for a future cohort, the subject may be rescreened.

## 5. STUDY VARIABLES

### 5.1 Pharmacokinetic Parameters

The PK parameters listed below will be calculated from the individual plasma and urine OP-101 concentration-time profiles. Additional PK Parameters may be added if it is necessary to fully describe the plasma and urine PK profile.

Variables	Description
$C_{max}$	Maximum observed concentration directly from data
$T_{max}$	Time to reach maximum observed concentration directly from data
$k_{el}$	Apparent terminal elimination rate constant
$t_{1/2}$	Terminal elimination half-life, calculated as $\ln(2)/\lambda_z$
$AUC_{0-last}$	Area under the concentration versus time curve from time zero to the last quantifiable concentration ( $C_{last}$ )
$AUC_{0-48}$	Area under the concentration versus time curve from time zero to 48 hour post dose time point
$AUC_{0-inf}$	Area under the concentration versus time curve from time zero extrapolated to infinity time
$CL/F$	Apparent total body clearance (as $Dose/AUC_{0-inf}$ ) after subcutaneous administration
$V_z/F$	Apparent volume of distribution (as $Dose/[\lambda_z * AUC_{0-inf}]$ ) after subcutaneous administration
$Ae_{0-48}$	Cumulative amount of unchanged study drug excreted into urine from Time 0 to 48 hours post-dose (Amount recovered in urine)

Variables	Description
%(Fe)	Fraction of the study drug excreted into urine in % (Fe) (as Ae/dose)
CL r	Renal clearance of the drug from plasma utilizing the AUC and Ae to the same duration (as Amount recovered /AUC at 0-48 hours)

## 5.2 Safety Variables

The following safety evaluations will be performed during the study:

- Adverse event monitoring
- Vital signs (pulse rate, BP, respiration rate, and temperature).
- Physical examination
- Clinical laboratory tests (hematology, chemistry, and urinalysis)

## 6. GENERAL STATISTICAL CONSIDERATIONS

### 6.1 Sample Size Determination

Up to 8 subjects will be enrolled and dosed in 2 cohorts with 4 subjects in each cohort who complete Day 15. The sample size in the study is based on clinical and practical considerations rather than statistical power.

### 6.2 Analysis Populations

#### 6.2.1 Safety Population

The Safety Population is defined as all subjects who received at least 1 dose of study drug.

#### 6.2.2 PK Concentration Population

The PK Concentration Population is defined as all subjects who received at least 1 dose of study drug and have at least 1 measurable concentration.

#### 6.2.3 Pharmacokinetic Parameter Population

The PK Parameter Population is defined as all subjects who received a dose of study drug and have at least 1 PK parameter.

## **7. STATISTICAL ANALYSIS**

### **7.1 General Considerations**

Continuous data will be summarized using descriptive statistics (number of subjects [n], mean, standard deviation [SD], percent coefficient of variation [%CV], median, minimum, and maximum). The geometric Mean (GM) and CV% GM will be also be added for Cmax and AUCs. Any subjects with a value of 0 for a parameter will be excluded from the calculation of GM and GM CV%.

Categorical data will be summarized using frequency counts and percentages.

### **7.2 Summary of Study and Subject Information**

#### **7.2.1 Subject Disposition**

Subject disposition information will be summarized by treatment in the Safety Population. Counts of subjects who receive any amount of drug as well as counts and percentages of subjects who complete each cohort and who withdraw early from the study will be presented in the summary table. The primary reasons for early withdrawal will also be included in the table. Percentages will be calculated using the number of Safety Population in each treatment as the denominator. Data will also be listed by treatment.

#### **7.2.2 Demographic and Baseline Characteristics**

Demographic and baseline characteristics include, but are not limited to, age at informed consent, sex, race, ethnicity, height, body weight, and body mass index (BMI). Height, body weight, and body mass index (BMI) will be collected at screening. If a value at the scheduled baseline is not available, the last measurement prior to the first dose of study drug will be served as the baseline value.

Demographic and baseline characteristics will be summarized by treatment based on Safety Population. Data will also be listed by treatment for all subjects in the Safety Population.

#### **7.2.3 Eligibility Criteria**

Eligibility criteria (inclusion/exclusion) will be listed for the Safety Population.

#### **7.2.4 Study Drug Administration**

Study drug administration data will be listed by treatment in the Safety Population.

### **7.2.5 *Prior and Concomitant Medications***

Prior and concomitant medications will be coded with the World Health Organization Drug Dictionary March 2018 Global B3 version.

Prior medications will be defined as those medications taken prior to the initial dose of study drug, and all medication taken on or after the first dose until the last PK sampling time in the last treatment period will be defined as concomitant medication.

All prior and concomitant medications will be listed and summarized for the Safety Population by treatment.

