5.6.2 Restricted Medications and/or Procedures

Subjects are not permitted to take prescription or non-prescription drugs (including vitamins and dietary or herbal supplements) within 14 days (14 days if the drug is a potential enzyme inducer) or 5 half-lives (whichever is longer) prior to the first dose of study medication until completion of the Day 15 Follow-up Visit, unless, in the opinion of the Investigator and Sponsor, the medication will not interfere with the study or is required out of medical necessity.

See Section 4.2 for exclusion criteria.

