5.6.5 Documentation of Prior and Concomitant Medication Use

All medications administered during the study must be documented on the concomitant medication eCRF.

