6.3 Treatment Period (Days 1 to 3)

6.3.1 Day 1

The following procedures will be performed on Day 1:

- Record prior and concomitant medications;
- Record vital signs (predose, 30 and 60 minutes and at 2, 4, and 12 hours after SC dosing);
- Collect urine sample for urinalysis predose;
- Obtain fasting blood sample for safety laboratory tests within 30 minutes prior to dosing;
- Administer study drug;
- Collect plasma PK samples (collected within 30 minutes prior to dosing, and at 30 minutes and 1, 2, 4, 6, 8, 10, 12, and 16 hours);
- Collect urine PK sample (within 60 to 30 minutes prior to dosing [spot sample] and between 0 to 4, 4 to 8, 8 to 12, 12 to 18, and 18 to 24 hours after dosing);
- Assess adverse events.

6.3.2 Day 2

The following procedures will be performed on Day 2:

- Record prior and concomitant medications;
- Perform physical examination;
- Record vital signs at 24 hours;
- Collect urine sample for urinary albumin, urinary creatinine, KIM-1, NGAL and urinalysis at 24 hours;
- Obtain fasting blood sample for safety laboratory tests at 24 hours;
- Collect plasma PK sample (24 and 30-36 hours after dosing);
- Collect urine PK sample (between 24 to 48 hours after dosing); and
- Assess adverse events.

6.3.3 Day 3

The following procedures will be performed on Day 3:

- Record prior and concomitant medications;
- Perform physical examination;
- Record vital signs at 48 hours;
- Collect urine sample for urinary albumin, urinary creatinine, KIM-1, NGAL and urinalysis at 48 hours;
- Collect plasma PK sample (48 hours after dosing);
- Collect urine PK sample up to 48 hours;
- Obtain fasting blood sample for safety laboratory tests at 48 hours;
- Assess adverse events; and
- Discharge subject from the investigational site.

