6.4 Follow-up Visit (Day 8)

The following procedures will be performed at the Follow-up Visit on Day 8:

- Record prior and concomitant medications;
- Perform physical examination;
- Record vital signs;
- Collect urine sample for urinary albumin, urinary creatinine, KIM-1, NGAL and urinalysis;
- Obtain fasting blood sample for safety laboratory tests; and
- Assess adverse events.

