9 APPENDICES

Table 1: SCHEDULE OF PROCEDURES-Cohort 1 and 2

Study Procedure	Screening Period		Check-In	Treatment Period			Follow-Up Visits [1]		Early Termination Visit
	Days -21 to -2	Day -1		Day 1	Day 2	Day 3	Day 8	Day 15	
Informed consent	X								
Admit to investigational site		X							
Inclusion/exclusion criteria	X	X							
Medical history	X								
Demographics	X								
Prior/concomitant medications	X	X	X	X	X [3]		X	X	X
BMI calculation [2]	X								
Physical examination (complete)	X	X	X	X	X [3]		X	X	
Vital signs [4]	X	X	X	X	X [3]		X	X	X
Breath alcohol screen	X	X	X						
Pregnancy test [5]	X	X	X						
FSH [5]	X								
Urine drug and cotinine screen	X	X	X						
Safety laboratory tests (chemistry, hematology, and urinalysis) [6]	X	X	X	X	X [3]		X	X	X
aPTT, PTT, INR	X								
HIV, HBsAg, HCVab screen	X								
Plasma PK sampling [7]			X	X	X [3]				
Urine PK sampling [8]			X	X	X [3]				
Administer study drug [9]									
Assess adverse events	X	X	X	X	X [3]		X	X	X
Discharge from investigational site									

A 30-minute window for vital signs and all postdose procedures is allowed.

When multiple procedures are scheduled at the same time point, the order of procedures should be as follows: obtain vital signs, collect blood sample (drawn at nominal time), and obtain urine sample.

1. There will be a  $\pm 1$ -day visit window for Days 8 and 15.
  2. Body weight and height will be measured at screening and used to calculate BMI.
  3. Assessments will be performed prior to discharge.
  4. Vital signs (pulse rate, respiration rate, body temperature, and BP) will be recorded at all study visits after the subject has been seated or supine for  $\geq 5$  minutes. During the Treatment Period, vital signs will be measured predose, 30 and 60 minutes and at 2, 4, 12, 24 and 48 hours after SC dosing.
  5. A serum (beta HCG) pregnancy test will be performed at screening for female subjects of childbearing potential only. A urine pregnancy test will be performed at Day -1 for female subjects of childbearing potential only. A test for FSH level will be performed only for women of non-childbearing potential who are not surgically sterile.

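### SAP 7.2.5 ends the concomitant-medication class at the last PK sample (about 48 h), so a drug first taken between then and Day 15 has no class, drops out of the summary and may be missed in the listing

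*SAP*

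**What the plan says.** SAP 7.2.5 sets up two classes. Prior medication is anything taken before the initial dose. For the other class, "all medication taken on or after the first dose until the last PK sampling time in the last treatment period will be defined" as concomitant. The output follows those classes: "All prior and concomitant medications will be listed and summarized for the Safety Population by treatment". There is no post-treatment or follow-up class.

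The last plasma sample falls, in SAP 3.2, "as well as on Day 3 (~48 hr") and, in protocol 6.3.3, on the same day: "Collect plasma PK sample (48 hours after dosing"). Urine PK collection also ends at 48 h.

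The protocol's treatment of medication runs longer:

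- Section 5.6.5: "All medications administered during the study must be documented on the concomitant medication eCRF".
- Sections 6.4, 6.5 and 6.6 (Day 8, Day 15 and Early Termination) each include the step "Record prior and concomitant medications".
- Section 5.6.2 keeps its restriction on other drugs in force "until completion of the Day 15 Follow-up Visit, unless, in the opinion of the Investigator and Sponsor, the medication will not interfere"; a second exception covers medical necessity.
- Section 9.2.8 plans a summary of concomitant medication and a listing of all medications with start and stop dates. Neither has a time limit.

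The SAP's own schedule (Appendix Table 1) has a row "Prior/concomitant medications" that is marked at the follow-up visits.

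**The concern.** The SAP rule stops well before medication recording stops. A drug first taken after the 48 h sample is recorded on the eCRF but is neither prior nor concomitant, so the SAP summary has no place for it. Read literally, the SAP listing has none either.

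Safety and tolerability are the primary objective, and the medication tables are context for reading those data. Adverse events are collected until participation ends (protocol 8.1), and eGFR, KIM-1 and NGAL are measured again on Days 8 and 15. Protocol 1.2 calls for careful assessment of renal function. It also reports that in the earlier IV study (20 and 40 mg/kg) KIM-1 and NGAL rose transiently, and that subjects with an increase at Day 15 had precautionary follow-up, after which values returned to baseline. Protocol 5.6.4 allows NSAIDs case by case during the study. Both documents also make other drugs part of the causality judgment for adverse events. A reader of late events or late renal markers needs medication data for the same period.

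**Working it through.** There is no stated figure to reproduce; the check compares the SAP's class limits with the schedule.

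**1. When the class closes.** The last PK sample is at 48 h nominal. Samples after 12 h may be taken within ±2 h (protocol 7), so the class closes between 46 and 50 h. The SAP's mention of a last treatment period does not move this point, because each subject has one dose and one Treatment Period, Days 1 to 3.

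**2. Length of the unclassified interval.** Day 15 is 14 × 24 = 336 h after a Day 1 dose. The visit window is ±1 day (protocol Appendix A, note 1), giving 312 to 360 h.

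| Case | Day 15 time − class closes | Interval | Share of dose-to-Day-15 time |
|---|---|---|---|
| Nominal | 336 − 48 | 288 h (12.0 days) | 288/336 = 85.7% |
| Shortest | 312 − 50 | 262 h (10.9 days) | 262/312 = 84.0% |
| Longest | 360 − 46 | 314 h (13.1 days) | 314/360 = 87.2% |

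**3. What is scheduled in that interval.**

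- Medication is recorded on Days 1, 2, 3, 8 and 15 from dosing on. Days 8 and 15 fall after the class closes: 2/5 = 40%.
- Post-dose eGFR, KIM-1 and NGAL are measured on Days 2, 3, 8 and 15 (protocol 8.6; Appendix A, note 6). Days 8 and 15 fall after: 2/4 = 50%.

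These counts describe the schedule. They do not measure bias, and a Day 8 record may concern a drug begun before 48 h.

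**4. Scale in the summary (assumption).** The documents give no expected medication use. Suppose the table reports the share of subjects with any concomitant medication, in a cohort of 4. Each subject whose only such drug was first taken after 48 h lowers that share by 1/4 = 25 percentage points, or 1/8 = 12.5 points over 8 subjects. For 0, 1 or 2 such subjects in a cohort, the shift is 0, 25 or 50 points.

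**5. Which drugs are affected.** A drug started by 48 h and continued is still concomitant. A drug that is not permitted would show in the deviation listing (SAP 7.2.7). That leaves mainly permitted drugs first taken between about 48 h and Day 15: a case-by-case NSAID, or a drug allowed under the exceptions in protocol 5.6.2.

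**The case against.** The strongest reply is that little is lost in practice. Protocol 9.2.8 still promises a listing of all medications, the SAP presents itself as an elaboration of the protocol, and listing specifications are in a separate document (SAP 1 and 8.2). With about 8 subjects, the dated listing is what one would use to interpret a late renal marker; a frequency table shows neither subject nor date. Few drugs should be involved, since subjects are healthy and medication is restricted to Day 15. The 25-point figure is only the weight of one subject in four. Ending the class with PK sampling could also be a deliberate exposure window, given the 5.5 h half-life and absence of detectable plasma drug after 24 h in the IV study.

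Much of this stands as a limit on size. Omission from the listing is a risk, not a certainty, and the percentage shift is only an illustration. But the protocol's listing does not restore the summary, which follows the SAP definition. The exposure-window reasoning appears nowhere in the SAP, SC kinetics are what this study is meant to measure, and such a window would not justify dropping drugs from a safety summary when the safety data run to Day 15. Protocol 9.2 requires departures from its planned analyses to be described in the SAP, and this one is not.

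**Conclusion.** The concern holds, as a minor one. Followed as written, SAP 7.2.5 leaves a drug first taken in the last 12 of the 14 days to Day 15 (nominal times) without a class and outside the medication summary, and puts its listing in doubt. This conflicts with protocol 5.6.5, 6.4 to 6.6 and 9.2.8 and with the SAP's own schedule.

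The effect is on the completeness of descriptive safety context. The data remain on the eCRF, and no analysis population, PK parameter or dose-escalation rule uses the definition. How many subjects would be affected cannot be derived from the documents and may be none. The conclusion rests on the literal wording of 7.2.5; the separate table and listing specifications were not available and could reduce the listing risk.

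**What to change.** In SAP 7.2.5:

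- Define concomitant medication as any medication taken on or after dosing through the Day 15 or Early Termination Visit. The present wording already covers drugs started before dosing and continued; saying so explicitly would help.
- Delete the reference to a last treatment period, which has no role in a single-dose design.
- State that every recorded medication is listed with start and stop dates, in line with protocol 9.2.8.

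If the sponsor wants to keep a class that ends with PK sampling, a separate post-treatment class running to Day 15 or Early Termination, also summarized and listed, would close the gap equally well.

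The cost is one definition and one listing sentence, with a matching check of the table and listing specifications. The data are already collected, so neither new data nor a protocol amendment is needed.
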